If the delivery system enters the subject's body in an attempt to place a device but no device is implanted during the initial procedure, the subject will be discontinued from the study after a 30-day adverse event collection period. This subject will be discontinued from the study even if Re-intervention occurs within the 30-day period.

If the subject signs a consent form, but the delivery system does not enter the subject, the subject will be considered a consented screen failure, for which a discontinuation form must be completed.

If a subsequent catheterization procedure is performed to attempt to close a residual shunt or new muscular VSD with an Amplatzer Muscular VSD Occluder, this will be classified as a Re-intervention. Data regarding Re-intervention(s) will be captured on new Baseline/Procedure forms for all subjects who meet Technical Success at the initial implant procedure. All follow-up visits will be calculated based on the initial procedure date.

Clinical Investigational Plan

Table 1: Main Data Requirements

	Pre-Procedure	Procedure	Post procedure (+ one day)	30 days (+/- 7 days)	6 Months (+/- 30 days)	One Year (+ 60 days)	Two Year (+/- 180 days)	Three Year (+/- 180 days)	Four Year (+/- 180 days)	Five Year (+/- 180 days)
Physical Exam	✓		✓	✓	✓	✓	✓	✓	✓	✓
ECG	✓		✓	✓	✓	✓	✓	✓	✓	✓
Echo ¹	✓		✓	✓	✓	✓	✓	✓	✓	✓
Cardiac catheterization		✓								
TEE or ICE		✓								
AE Assessment		✓	✓	✓	✓	✓	✓	✓	✓	✓
Chest X-ray AP and lateral	✓		✓			✓	✓	✓	✓	✓
Fluoroscopy ²						✓	✓	✓	✓	✓

¹ Echocardiographic data at Baseline/Procedure can include TTE, TEE and/or ICE.

Echocardiographic image data must be submitted to the sponsor for one year visits.

² Fluoroscopy required if chest x-rays are read as “uncertain” with regard to wire fracture.

1. Implant Procedure

Reference the Amplatzer Muscular VSD Occluder and Delivery System Instructions for Use (IFU) for implant procedure techniques. The Amplatzer Muscular VSD Occluder is to be implanted percutaneously by catheter technique.

2. Closure Assessment

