Assessment of VSD closure will be conducted post device deployment during the procedure, at the post procedure follow-up visit, at the 30-day follow-up visit, at the six month follow-up visit, at the one year follow-up visit and at annual visits until the five year visit is complete. Investigators are required to record echocardiographic data to document closure status and submit the data to the sponsor on case report forms in the remote data entry system. An independent Echocardiography Board or Core Laboratory will review the one-year echocardiograms to verify closure status.

3. Follow-up Compliance Measures

Abbott (ABT) will have a dedicated staff to train and manage sites on the importance of protocol compliance, assist sites with reminders, and compensate sites to help ensure adequate subject follow-up. ABT will send reminders to each site regarding upcoming visits. Each enrolled subject will receive a visit notification card. Whenever possible, the site should schedule the next subject follow-up visit at the time of the current visit. Sites will be compensated for the time it takes for the investigator to complete the case report forms. As part of CRF completion reimbursement, sites will be compensated for time spent notifying and reminding subjects of upcoming follow-up visits. If a site becomes non-compliant, enrollment may be halted until the site initiates the appropriate steps to correct compliance.

Clinical Investigational Plan**4. Device Explant**

If a subject has a device explanted during the study, the timing of the explant determines whether the subject is followed further or discontinued from the study. If the device explant occurs before the 12-month visit and a Serious Adverse Event (SAE) is associated with the device explant, the subject will be discontinued on the date the device is explanted. (In this case, the subject is considered a failure for all endpoints except Technical Success.) If a device explant is not associated with a SAE, the subject will continue to be followed through the 12-month visit. The subject will then be discontinued at the 12-month visit.

If a subject has a device explanted after the 12-month visit, the subject will be discontinued on the date of the explant procedure.

J. Adverse Event Reporting

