Safety surveillance and reporting starts as soon as the patient is enrolled in the clinical study. Safety surveillance and reporting will continue until the last follow-up visit has been performed, the subject is deceased, the subject concludes participation in the clinical study or the subject withdraws from the clinical study.

For subjects that do not receive a device

If the delivery system enters the subject's body in an attempt to place a device but no device is implanted, the patient will be followed for reportable adverse events for 30 days. The subject should attend a 30-day (+/- 7 days) visit for an adverse event assessment and then be discontinued.

Adverse event data will be collected throughout the time period defined above and will be reported to the Sponsor on a CRF. Additional information with regard to an adverse event should be updated within the appropriate CRF.

For the purposes of this study, the following event types will be reported:

- All serious adverse events

SAE Reporting

The investigator should report all SAEs to the Sponsor as soon as possible but no later than outlined below. For retrospective subjects, the reporting timeframe does not apply to SAEs that occur prior to the informed consent date.

Clinical Site	Reporting timelines
---------------	---------------------

Clinical Investigational Plan

All Sites	SAEs must be reported to the Sponsor no later than 3 calendar days from the day the site personnel became aware of the event or as per the investigative site's local requirements, if the requirement is more stringent than those outlined above.
-----------	---

The date the site staff became aware the event met the criteria of an SAE must be recorded in the source document. The Investigator will further report the SAE to the local IRB/EC according to the institution's IRB/EC reporting requirements.

K. Study Duration

This study will enroll [REDACTED] Each study subject receiving a device will be followed for 60 months post-procedure, unless the device is explanted (See Section I.5 regarding Device Explant).

Clinical Investigational Plan**II. Statistical Analysis**

Analysis will include prospectively and retrospectively enrolled subjects, unless otherwise specified.

The primary safety objective is to evaluate the proportion of subjects experiencing a serious adverse event within 12 months of the procedure. [REDACTED]

[REDACTED]

[REDACTED]

[REDACTED]

[REDACTED]

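### SAEs and deaths after an SAE-associated explant before 12 months, or after any explant beyond 12 months, are not collected; descriptive safety counts can be too low, but the primary SAE rate is unaffected

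*Protocol*

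**What the plan says.** Protocol I.I.4 (Device Explant) has three branches:

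- **Before the 12-month visit, SAE associated with the explant:** "the subject will be discontinued on the date the device is explanted". On scoring it adds: "In this case, the subject is considered a failure for all endpoints except Technical Success".
- **Before the 12-month visit, no associated SAE:** "If a device explant is not associated with a SAE, the subject will continue to be followed through the 12-month visit". The subject leaves at that visit.
- **After the 12-month visit:** "the subject will be discontinued on the date of the explant procedure".

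Protocol I.J lets safety surveillance run only until the last visit, death, withdrawal or the end of participation. For a subject in whom an implant was attempted but no device was placed, I.J says that "the patient will be followed for reportable adverse events for 30 days".

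Protocol I.I treats that same group as follows: "the subject will be discontinued from the study after a 30-day adverse event collection period", and then: "This subject will be discontinued from the study even if Re-intervention occurs within the 30-day period". Protocol I.K, by contrast, states: "Each study subject receiving a device will be followed for 60 months post-procedure", with explant as the only exception. SAP 3.0 says the same.

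SAP 5.2 lists deaths and device- and procedure-related events as descriptive endpoints. SAP 6.3 reports the number of deaths, and SAP 6.4 the number of events and the percentage of subjects with events.

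**The concern.** Before 12 months, follow-up is shortest for the subjects whose explant came with a serious event. They have no collection after the explant date. A subject explanted without an SAE is followed to the 12-month visit, and a subject who never had a device is followed for 30 days. The documents give no reason for this ordering.

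The days after device removal are a period in which a device- or procedure-related SAE or a death could plausibly occur. The study's stated purpose is to evaluate safety further, so the completeness of its death and device-related event counts is at stake. A second, separate question is whether a subject who receives a device at a second attempt within 30 days is followed for 30 days or for 60 months, since the documents support both answers.

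**Working it through.** **1. The plan's own figure.** SAP 5.3 asks for 80 evaluable subjects and enrols 100. With 20% attrition, inferred from the 80% follow-up level in SAP 3.0, 80 / (1 − 0.20) = 100, which matches. The basis for the 80 is not readable. On this scale, 1 to 5 explants would be 1% to 5% of subjects.

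**2. Effect of each explant branch on the primary endpoint.** The endpoint is binary: any SAE within 12 months of the procedure (SAP 4.1).

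| Explant branch | Status in the primary analysis | Change if followed longer |
|---|---|---|
| Before 12 months, SAE-associated | already a failure | 0 |
| Before 12 months, no SAE | already followed to 12 months | 0 |
| After 12 months | outside the window | 0 |

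**3. Effect on the descriptive counts.** An event that is not collected can only lower a count or leave it unchanged. A subject with an early SAE-associated explant already has an SAE, so the percentage of subjects with any SAE does not move for that group. The number of events, the number of deaths and the device- and procedure-related categories can move. For late explants, the percentage with any SAE over five years can move as well.

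**4. Illustrative size.** The readable text gives neither the number of same-day exits (k) nor the risk of death in the 30 days after explant (q). Both are assumptions here, and subjects are taken as independent. Expected missed deaths = k × q; chance of missing at least one = 1 − (1 − q)^k.

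| k | q = 5%: expected | q = 5%: at least one | q = 10%: expected | q = 10%: at least one |
|---|---|---|---|---|
| 1 | 0.05 | 5.0% | 0.10 | 10.0% |
| 3 | 0.15 | 14.3% | 0.30 | 27.1% |
| 5 | 0.25 | 22.6% | 0.50 | 41.0% |

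For example, 1 − 0.95^5 = 1 − 0.774 = 0.226, and 1 − 0.90^5 = 1 − 0.590 = 0.410. With no such explants the loss is zero.

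**5. The Re-intervention conflict.** Protocol I.I defines a Re-intervention as a further catheter attempt with the study device. If it succeeds after a failed first procedure, the subject has received a device and falls under both the 30-day rule in I.I and the 60-month rule in I.K and SAP 3.0. I.I provides Re-intervention forms only for subjects with technical success at the first procedure, so no form is stated for this second procedure.

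Unlike explant, this group can touch the primary result. Protocol II analyses subjects with a 12-month visit or an earlier SAE, so a subject who leaves at 30 days without an SAE drops out of the set. Assume 40 SAEs in 80 subjects (50.0%) and restore such subjects, with none or all of them having an SAE:

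- 1 subject: 40/81 = 49.4% to 41/81 = 50.6%.
- 5 subjects: 40/85 = 47.1% to 45/85 = 52.9%.

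An exact one-sided binomial test against the 63.2% in SAP 5.1.1.1 allows at most 41 of 80 or 44 of 85 SAEs at an assumed level of 0.025, and 42 of 80 or 45 of 85 at 0.05. So 45/85 fails at 0.025 and just passes at 0.05; the conclusion could change only near the boundary. The direction is uncertain: leaving out SAE-free subjects raises the observed rate, while missing their SAEs after day 30 lowers it.

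**The case against.** The strongest reply is that ending follow-up at explant is an openly stated design choice. Protocol I.K and SAP 3.0 both make explant the exception to 60-month follow-up, so on explant nothing is contradicted. Once the device is out, a device study has less reason to continue, no hypothesis test is affected, and the 30-day period is borrowed from a different situation, the failed implant. All of this stands, and it is why the point is minor. It does not explain why a failed implant has 30 days of collection and an SAE-associated explant none.

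A reader might infer more than the documents support:

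- **That every explanted subject leaves on the day of explant.** Not so: an explant before 12 months without an associated SAE is followed to the 12-month visit.
- **That events around explant are never counted.** Too strong. Events up to and including the discontinuation date are collected, and I.J asks for later information on an event to be added to its CRF, so the outcome of an SAE already reported, possibly including death, may still be recorded. I.I.4 also speaks of an SAE associated with the explant, which could include one caused by it. What remains uncollected is a new SAE or death after that date.

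On Re-intervention, I.I addresses the case expressly and can be read as a specific exception to the general sentence, or I.K can be read as meaning a device placed at the first procedure. Either reading would remove the conflict, but neither I.K nor SAP 3.0 says so.

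SAP 5.1.1.4 and 5.1.1.5 are not readable and may settle how such subjects are analysed. Neither they nor the last-known-status analysis in Protocol II can recover events that were not collected.

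**Conclusion.** The point holds as a minor gap in data collection. It covers SAE-associated explants before the 12-month visit and all explants after it. For these subjects, new SAEs and deaths after the explant date are lost by rule, and the counts in SAP 5.2, 6.3 and 6.4 can be too low but not too high.

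A reader might go further and conclude that the primary safety rate is understated. The documents do not support that for explant: the change is zero in all three branches.

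The size is unknown. The 5% to 41% chance of missing at least one death rests entirely on the assumed 1 to 5 explants and 5% to 10% risk, and shows only what such numbers would imply.

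The Re-intervention conflict is real but narrow. It arises only if a second attempt within 30 days places a device, and its frequency is not given.

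**What to change.** In Protocol I.I.4, continue SAE and vital-status collection for 30 days after explant, by contact or chart check, as I.J already does for failed implants. State in SAP 5.2, 6.3 and 6.4 that these events are included.

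Separately, reconcile the 30-day discontinuation rule in Protocol I.I with Protocol I.K and SAP 3.0 for subjects who receive a device at a second attempt, and state how their second procedure is recorded and their later SAEs counted. In the same edit, correct the cross-reference in I.K, which points to item 5 for device explant although the text is item 4.

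The cost is protocol and SAP wording plus one contact or chart check for what is likely to be a handful of subjects. Reported death and event counts may rise slightly. The change concerns data collection only, not clinical care.

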A serious adverse event is defined as any untoward medical occurrence that:

- results in death;
- is a life-threatening adverse event;
- requires inpatient hospitalization or prolongation of existing hospital stay;
- results in persistent or significant disability/incapacity;
- results in congenital anomaly/birth defect;
- or results in a medically significant event, including laboratory abnormalities.

Primary Effectiveness Objectives

The effectiveness objective is to evaluate the proportion of subjects who experience technical success, closure success, and acute procedure success. Results for the three effectiveness endpoints will be reported separately and, like the safety endpoint, will be compared for non-inferiority against the corresponding results of the High Risk Cohort of the Muscular VSD Occluder Study.

Technical Success

Technical success is met for implant attempt subjects in whom a device is successfully deployed in the ventricular septal defect.

Acute Procedure Success

Acute procedure success is met for implant attempt subjects who meet shunt closure success (as defined in the next paragraph) at procedure.

Shunt Closure Success

Shunt Closure Success is met for subjects in whom the defect has less than or equal to two millimeters residual shunt. Shunt Closure Success will be evaluated at the post procedure, 30 day, 6-month, 12-month and annual follow-up visits through 5 years. The effectiveness endpoint for Shunt Closure Success will be based on the evaluation of the one year follow-up visit.

Clinical Investigational Plan

G. Eligibility Criteria

A subject is eligible to participate in the study if he/she meets all inclusion criteria and none of the exclusion criteria.

Patients who previously received an Amplatzer Muscular VSD Occluder following device approval on September 7, 2007, may be eligible to enroll in the study. Refer to **Section I, Part H.** for details.

Inclusion Criteria

1. The Amplatzer Muscular VSD Occluder is indicated for use in subjects with complex congenital muscular ventricular septal defects (VSD) of significant size to warrant closure. Subjects must meet at least one of the following:
 - a. Large volume left to right shunt ($Q_p/Q_s > 2:1$),
 - b. Pulmonary hypertension (PA pressure $> 50\%$ systemic),
 - c. Clinical symptoms of congestive heart failure,
 - d. Banding of the pulmonary artery(ies) and in the opinion of the treating investigator closure of the VSD is clinically warranted.

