Similarly, the three effectiveness objectives are the proportion of subjects who experience technical success, acute procedure success, and shunt closure success. In

[REDACTED]

Note: technical success analysis will include only prospectively enrolled subjects.

[REDACTED]

[REDACTED]

Clinical Investigational Plan

[REDACTED]

[REDACTED]

[REDACTED]

[REDACTED]

[REDACTED]

[REDACTED]

The analysis of technical success and acute procedure success will be conducted on all subjects who have an attempted device placement (defined as the delivery system enters the subject's body in an attempt to place a device). The analysis of shunt closure success will be conducted on the study population who has a 12-month follow-up visit. The serious adverse event endpoint will be evaluated on all subjects who have a 12-month follow-up visit or who had a serious adverse event prior to the 12-month visit. For all analyses, a secondary analysis will be conducted on the entire study population, including subjects that are classified as lost to follow-up. In the situation classified as lost to follow-up, subject's last known (reported) status will be used in the calculations.

[REDACTED]

[REDACTED]

Clinical Investigational Plan**III. Study Management****A. Investigators and Sites**

A list of institutions and investigators will be completed and sent to the FDA or other regulatory authorities upon request and as required by applicable regulations.

B. Monitoring Procedures

Monitoring will be conducted according to the ABT Clinical Monitoring standard operating procedure.

Prior to beginning the study, ABT will contact the investigator or designee to discuss the study and data requirements. An ABT monitor will periodically review the subject records and associated source documents.

The investigator shall make subject and study records available to the clinical monitor for monitoring.

C. Data**1. Source Data and Documentation**

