Written documentation of IRB/EC approval for the protocol and sponsor-approved informed consent including HIPAA authorization for the study must be received by ABT prior to enrollment of subjects. The IRB/EC must review and approve the continuation of the study at a minimum of annually from the initial approval date until the study is officially closed out at a site.

4. Approval to Enroll

Investigators must receive written approval from ABT prior to enrolling study subjects.

F. Review Boards**1. CEC**

An independent Clinical Events Committee (CEC) will be utilized to adjudicate reported adverse events. Members of the CEC will have no affiliation with the Muscular VSD Clinical Study. This committee will be composed of at least three

Clinical Investigational Plan

clinicians with expertise in VSD closure. The CEC will review and adjudicate events reported by investigators as defined in the CEC charter.

2. Echocardiography Board

An independent Echocardiography Board or Core Laboratory will review one year echocardiograms to verify closure status. The Board or Core Laboratory may also evaluate echocardiographic images as necessary for analysis of endpoints.

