4.2.3 Primary Effectiveness Endpoint 3: Shunt Closure Success

Primary effectiveness endpoint 3 is the proportion of subjects who have shunt closure success. Shunt closure success is defined as a defect with \leq two millimeters residual shunt at the one-year follow-up visit.

4.3 **Descriptive Endpoints**

The trial has a number of descriptive endpoints. See Sections 5.2 for a full listing.

5.0 **STATISTICAL METHODS**

5.1 **Primary Endpoints**

This trial has one primary safety endpoint and three primary effectiveness endpoints.

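### A device explanted before 12 months can still count as a shunt closure success, and explants the protocol calls failures can drop out of the closure denominator

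*Protocol*

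**What the plan says.** **Explants before 12 months (Protocol I.I.4).** If an SAE is associated with the explant, the subject is discontinued on the explant date, and "In this case, the subject is considered a failure for all endpoints except Technical Success". Otherwise, "If a device explant is not associated with a SAE, the subject will continue to be followed through the 12-month visit", after which the subject is discontinued. No endpoint status is given for this second group. The section does not define when an SAE is associated with an explant, or say who decides.

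**Closure endpoint.** Protocol I.F: "Shunt Closure Success is met for subjects in whom the defect has less than or equal to two millimeters residual shunt". The primary evaluation is at one year, and SAP 4.2.3 and 5.1.2.3 use the same criterion ("two millimeters residual shunt at the one-year follow-up visit"). None of these requires the study device to be in place or mentions closure by other means.

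**Closure analysis set (Protocol Section II).** "The analysis of shunt closure success will be conducted on the study population who has a 12-month follow-up visit".

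**SAEs.** One SAE criterion in Protocol I.F is an untoward occurrence that "requires inpatient hospitalization or prolongation of existing hospital stay". Protocol I.J asks sites to report SAEs only. Under Protocol III.F, "The CEC will review and adjudicate events reported by investigators as defined in the CEC charter"; the charter is not among the documents.

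**The concern.** Whether an SAE accompanied the removal of a device says nothing about whether that device closed the defect. Yet on the readable text the SAE label decides whether the explant itself makes the subject a closure failure. If the label is absent and the defect was then closed by a patch or another product, the one-year echocardiogram shows 2 mm or less and the subject is a success. Independent echo review does not prevent this, because its stated task is to verify closure status, not to establish what closed the defect.

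The other branch has a separate problem. The subjects that I.I.4 calls failures are discontinued at explant, so no 12-month visit is expected, and Section II admits only subjects who have one. One passage counts them as failures and the other removes them.

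At stake is the one-year closure rate, a primary effectiveness endpoint tested against a goal derived from the High Risk Cohort.

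**Working it through.** **Step 1. Follow each kind of subject through the readable rules.**

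| Subject before 12 months | Status in I.I.4 | 12-month visit? | In closure set (Section II)? | Closure result |
|---|---|---|---|---|
| Explant, SAE associated | Failure | Not expected (discontinued) | No, read literally | Failure or excluded: passages conflict |
| Explant, no associated SAE, shunt > 2 mm at one year | None stated | Yes | Yes | Failure |
| Explant, no associated SAE, defect closed otherwise to ≤ 2 mm | None stated | Yes | Yes | **Success** |

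The third row also covers a subject whose SAE is judged not to be associated with the explant. That subject counts as an event for safety, but closure can still be a success.

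**Step 2. Inputs.**
- Closure goal: 58.7% (SAP 5.1.2.3).
- Evaluable n: 80, enrolled 100 (SAP 5.3). With the 80% follow-up figure in SAP 3.0, 80 / 0.80 = 100, so the plan's enrolment figure reproduces. The 80 itself cannot be checked, because the assumed rates, level and power are redacted.
- Assumptions: exact one-sided binomial test at 5% or 2.5%; closure set of 80; explant numbers as stated below.

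**Step 3. Critical counts.** p(x, n) = P(X ≥ x), with X ~ Binomial(n, 0.587).

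| x/n | Rate | p | Passes 5% | Passes 2.5% |
|---|---|---|---|---|
| 54/80 | 67.50% | 0.0674 | no | no |
| 55/80 | 68.75% | 0.0419 | yes | no |
| 56/80 | 70.00% | 0.0247 | yes | yes |

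**Step 4. Explant scored as success.** Each subject moved from failure to success adds 1/80 = 1.25 percentage points. At either level, rescoring one subject at the critical count reverses the result: 55 to 54 at 5%, 56 to 55 at 2.5%. If the correct alternative were exclusion rather than failure, the gain is smaller: 54/79 = 68.35% against 55/80 = 68.75%, or 0.4 points.

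**Step 5. SAE explants dropped from the denominator.** Take 54 successes with the SAE explants among the non-successes.
- Kept as failures: 54/80, p = 0.0674.
- One dropped: 54/79 = 68.35%, p = 0.0502, up 0.85 points.
- Two dropped: 54/78 = 69.23%, p = 0.0365, which passes at 5%.

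With 55 successes at the 2.5% level, the same sequence is p = 0.0419 (55/80), 0.0301 (55/79) and 0.0211 (55/78), so again two dropped subjects turn a miss into a pass.

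**Step 6. Effect on type I error of the scoring in Step 4.** Suppose the true success rate, with explants as failures, equals 58.7%, and a share q of all subjects is scored success instead. The rejection probability is P(X ≥ c), with X ~ Binomial(80, 0.587 + q).

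| q (assumed) | c = 55 (nominal 5%) | c = 56 (nominal 2.5%) |
|---|---|---|
| 0 | 0.042 | 0.025 |
| 1% | 0.061 | 0.037 |
| 2.5% | 0.101 | 0.065 |
| 5% | 0.206 | 0.145 |

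**The case against.** **Redaction.** The SAP text on the safety population, the safety sensitivity analysis, and the closure population and sensitivity analysis is blank or cut off, as is much of Protocol Section II. An explant rule could sit there. This stands: the gap can be asserted only for the readable text. However, the closure definitions, I.I.4 and the Section II population sentence are readable, and they contain no such rule.

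**Few subjects.** The gain needs an explant, no associated SAE, and a defect otherwise closed to 2 mm or less. The documents give no explant count, so the number affected may be zero. This also stands, and the sizes above are conditional on it.

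**Secondary analysis.** Section II adds an analysis of the entire study population. That could bring back the discontinued SAE explants, but it is secondary and does not change how a non-SAE explant is scored.

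**Comparability.** The endpoint is to be compared with its counterpart in the High Risk Cohort, whose explant scoring is not shown. Changing the rule on one side only could harm the comparison. This stands and is met in the fix.

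**A stronger reading the documents do not support.** A reader might infer that these subjects are also wrongly counted as SAE-free, on a site's say-so. A subject with no SAE is correctly SAE-free. Removal in hospital would usually meet the hospitalization criterion, and such an SAE, if associated with the explant, already makes the subject a failure under I.I.4. That section is conditional: it neither changes the SAE definition nor gives the decision to the site. What remains is narrower. The association is undefined, and an explant not reported as an SAE need not reach the CEC on the readable text.

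**Conclusion.** The point holds for Shunt Closure Success, with medium confidence because of the redactions. On the readable text, a subject without the study device can be counted as its one-year success, and I.I.4 and Section II disagree on whether SAE-associated explants are failures or excluded. Both favour the device. Each subject scored success rather than failure is worth 1.25 points at n = 80, and one can decide a borderline result; each SAE explant dropped is worth about 0.85 points near the critical value. These sizes rest on an assumed exact one-sided test, assumed levels of 5% and 2.5%, a closure set of 80, and unknown explant numbers.

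It would go too far to say that only SAE-associated explants can fail closure, since a non-SAE explant with more than 2 mm residual shunt at one year fails under the ordinary definition. No bias in the primary safety endpoint is shown.

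**What to change.** In Protocol I.I.4, Protocol Section II, and SAP 4.2.3 and 5.1.2.3, state for analysis purposes:

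1. Any explant of the study device, or closure of the treated VSD by surgery or a non-study product, before the 12-month visit is a failure for Shunt Closure Success, whether or not an SAE is reported.
2. These subjects stay in the closure denominator even without a 12-month visit. Without this sentence, the failures declared in item 1 could still fall outside the analysis set.
3. If the High Risk Cohort's closure endpoint was scored differently, the result is also reported under that cohort's rule.
4. Every explant goes to the existing CEC, which decides whether the protocol's SAE definition is met and whether the SAE is associated with the explant. The protocol defines that association.

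These are scoring and adjudication rules; follow-up and discontinuation need not change. If redacted text already covers explants, it should be cross-referenced from I.I.4 and Section II.

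The cost is a few sentences in two documents and a few more cases for the CEC. The closure rate may become slightly less favourable.
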